## 6.3.3 Safety Analysis

All subjects entered into the study at Visit 1 will be included in the safety analysis. Safety will be monitored by adverse event reporting. The frequencies of AEs by type, body system, severity and relationship to study drug will be summarized. SAEs (if any) will be described in detail.

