## 5.3 Safety Evaluation

Safety will be monitored by adverse events reporting. The frequencies of AEs by type, body system, severity and relationship to study supplement will be summarized. SAEs (if any) will be described in detail.

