## 6.3.2 Efficacy Analysis

Descriptive statistics for CFA%, duodenal pH, MBT and QOL outcomes (mean, standard deviation, median, range, 95% CI) will also be calculated for the total group comparing on and off omeprazole treatment using pair t-tests or Wilcoxon sign rank tests as appropriate. Changes within randomization groups over time will also be explored using paired t tests Differences between randomization groups (12 randomized initially to placebo vs. 12 to omeprazole treatment) on visit 1 will also be tested using unpaired t tests or Mann Whitney U rank sum test as appropriate. Significance of the differences on and off treatment assessed with paired t tests or Wilcoxon sign rank tests as appropriate. PK parameters can then be compared for the total group comparing on and off omeprazole treatment using pair t-tests or Wilcoxon sign rank tests as appropriate, and between randomization groups at each time point using an unpaired t-test or Mann Whitney U rank sum test as appropriate. Alternately, population PK analyses for repeated-measures endpoints can be conducted via nonlinear mixed-effects modeling with a qualified installation of the nonlinear mixed-effects modeling (NONMEM) software, Version VII, Level 2.0 (ICON Development Solutions, Hanover, MD). HA and PA concentrations will be transformed to molar quantities and the ratios for HA to PA Cmax and AUC and the associated 95% confidence interval will be calculated. A mixed-effects modeling approach will be employed to examine the correlation of subject characteristics (age, BMI, sex, disease status, etc) to CFA%, duodenal pH, QOL parameters and to PA and HA exposure metrics derived from the non-compartmental analysis to assess change over time in MBT response to PERT administration in subjects with CP. Metrics to be tested will be CFA%, duodenal pH, QOL parameters, PA and HA Cmax, AUC, HA/PA Cmax and AUC ratio and the %HA response comparing subjects when on or off omeprazole treatment and also comparing randomization groups at each time point. A value of p<0.05 will be considered statistically significant.

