We have not based the samples size upon the secondary exploratory hypotheses, however, the effect sizes that can be detected with our sample size of 22 subjects can be estimated. For the MBT method, the sample size is based upon our previous experience in CF with detecting differences in Cmax and AUC for HA and the HA/PA ratio4, and in detecting the percent change in HA absorption (from pharmacokinetic modeling) compared to healthy subjects5. For our proposed study, with the crossover design, 22 subjects (11 in each randomization group) will have 80% power to detect a difference in means of 0.60 (the difference in Cmax (in AUC) HA/PA ratio, with a mean of 1.62 (1.30) for omeprazole treatment, compared to 1.02 (0.70)) for placebo: this is a 37% increase in Cmax and 46% increase in AUC with omeprazole treatment compared to placebo, assuming that the common SD is 0.68 using a paired t-test with  $\alpha$  =0.05. For the CFQ-R domain scores, a sample size of 22 subjects with provide 80% to see an increase of 9 points (i.e. from 80 to 89) with omeprazole treatment compared to placebo with a common SD of 15 points using a paired t-test with  $\alpha$ =0.05. For the SmartPill®, Gelfond has demonstrated significantly lower duodenal pH in subjects with CF compared to healthy controls. The outcome of interest is the time that it takes for the pH to reach 5.5, the minimum level required to dissolve the enteric coating from PERT so that they are effective for nutrient absorption. In a study of 10 subjects with CF compared to 10 healthy controls using the SmartPill® methodology, the time required to reach a pH of 5.5 in CF was 17.7±6.8 compared to  $6.3\pm6.4$  In controls (p=0.004). We expect a subsample of 12 subjects to be 18+ years of age and use the SmartPill® for duodenal pH assessment. A sample of 10 subjects is required for 80% power to see a reduction in time to pH of 5.5 in the GI tract from 17 to 11 minutes

with omeprazole treatment compared to placebo, with a common SD of 7 minutes, using a paired t-test with  $\alpha$ =0.05.

Using this randomized crossover design, a total sample of 22 subjects, 11 in each randomization group will be needed. Therefore, enrolling 24 subjects (12 in each group) will result in 22 subjects completing the study if we experience 10% attrition.

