## 8.3 Definition of an Adverse Event

An adverse event is any untoward medical occurrence in a subject who has received an intervention (drug, biologic, or other intervention). The occurrence does not necessarily

have to have a causal relationship with the treatment. An AE can therefore be any unfavorable or unintended sign (including an abnormal laboratory finding, for example), symptom, or disease temporally associated with the use of a medicinal product, whether or not considered related to the medicinal product.

All AEs (including serious AEs) will be noted in the study records and on the case report form with a full description including the nature, date and time of onset, determination of non-serious versus serious, intensity (mild, moderate, severe), duration, causality, and outcome of the event.

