## 8.6 Investigator Reporting of a Serious Adverse Event to Sponsor

Reporting will be consistent with regulatory and sponsor requirements. All serious adverse events experienced by a study subject receiving omeprazole will be reported to the sponsor, Chiesi USA, Inc., within 24 hours of learning of the event regardless of the relationship of the event to omeprazole. The PI shall make available to Chiesi USA, Inc., promptly such records as may be necessary and pertinent to investigate any such event, if specifically requested by Chiesi USA, Inc. For medical emergencies, we will follow the CHOP procedures for medical emergencies that may occur for adult visitors to CHOP.

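### The AE summary is not split by treatment received in a crossover, and the 24-hour sponsor SAE rule in 8.6 turns on an allocation that blinded staff do not know

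*Combined protocol and SAP*

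**What the plan says.** **AE analysis.** Section 6.3.3 defines the safety set: "All subjects entered into the study at Visit 1 will be included in the safety analysis". It then gives the summary: "The frequencies of AEs by type, body system, severity and relationship to study drug will be summarized". Section 5.3 has the same four dimensions ("The frequencies of AEs by type, body system, severity and relationship to study supplement will be summarized"), as does the safety entry in the synopsis. None of the three places names treatment, period or sequence. For efficacy, 6.3.2 does name the contrast: outcomes are "calculated for the total group comparing on and off omeprazole treatment using pair t-tests or Wilcoxon sign rank tests". AEs are not among the metrics listed there.

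**AE data.** Section 8.3 requires each AE to be recorded "with a full description including the nature, date and time of onset, determination of non-serious versus serious". It also restricts the term: "An adverse event is any untoward medical occurrence in a subject who has received an intervention".

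**SAE reporting.** Section 8.6 says: "All serious adverse events experienced by a study subject receiving omeprazole will be reported to the sponsor", within 24 hours and whatever the judged relationship. The Data and Safety Monitoring Plan in the synopsis and section 9.4.1 also send SAEs to the sponsor, without regard to arm, but state no time limit. The time limits in 8.5 apply to the IRB.

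**Blinding.** Section 9.1.2 blinds all study personnel throughout. Sections 3.2, 7.1.1 and 9.1.3 provide for unblinding in an emergency or when clinically necessary.

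**The concern.** Every completer takes both capsules. An AE table without a treatment dimension therefore cannot show which events arose on omeprazole, which on placebo and which on neither. The relationship column does not fill the gap, because blinded staff make that judgement. The safety set is also fixed at Visit 1, before any dose, so it may include people who never took omeprazole, and no denominator per treatment is given.

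The clause in 8.6 is a different problem: its trigger depends on information that the people who must apply it do not have. At stake are a consistent sponsor deadline for SAEs in all periods, and the absence of any reason to seek the code for an administrative purpose.

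**Working it through.** The plan states no figure on this point, so there is none to reproduce. The check counts days in the study flow table (section 4.1) and then compares the reporting clauses.

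**1. How much of the pooled AE time is omeprazole time**

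Inputs from the flow table: treatment on Days 16-43 and 65-92, assessment blocks on Days 44-50 and 93-99, washout on Days 51-64.

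- First dose to last collection: 99 − 16 + 1 = 84 days. Check: 28 + 7 + 14 + 28 + 7 = 84.
- Omeprazole days per subject depend on when dosing stops:
  - 28 days per period (flow table): 28/84 = 33.3%
  - the whole 33-day supply taken (7.1.1): 33/84 = 39.3%
  - dosing through the assessment block: (28 + 7)/84 = 35/84 = 41.7%
- Days not on omeprazole: 84 − 35 = 49 to 84 − 28 = 56.

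Illustration, assuming a constant background AE rate that omeprazole doubles or triples. The pooled rate relative to background is (d × RR + 84 − d)/84, where d is omeprazole days.

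- RR = 2: (56 + 56)/84 = 1.33 for d = 28; (70 + 49)/84 = 1.42 for d = 35.
- RR = 3: (84 + 56)/84 = 1.67 for d = 28; (105 + 49)/84 = 1.83 for d = 35.

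Pooling dilutes the signal, and the pooled table has no placebo column to compare it with.

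**2. Whether the split can be made from the planned data**

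Yes for most days, because 8.3 records onset date and time. The exception is the two assessment blocks: 7 + 7 = 14 days, 14/84 = 16.7%. The documents differ on dosing status there:

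- The flow table ends 28-day treatment on Days 43 and 92.
- Section 3.1.3 starts the washout, with study drug stopped, after the second visit is completed.
- Section 4.5 stops omeprazole once all Visit 3 collections are complete.
- Section 7.1.1 supplies 33 days of drug for 28 days of use. Dosing on Days 16-50 would need 35 doses.

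**3. Denominators and expected counts**

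Section 6.4 plans that "enrolling 24 subjects (12 in each group) will result in 22 subjects completing the study if we experience 10% attrition". The number ever dosed with omeprazole would then be 22 to 24. Section 9.4.2 puts the listed events at fewer than 7% of patients. Read as a rate per event, that is fewer than 0.07 × 22 = 1.54 to 0.07 × 24 = 1.68 subjects each. Counts this small support description, not testing.

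**4. Sponsor SAE reporting, by time of onset, reading 8.6 literally**

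| Onset | Can blinded staff apply 8.6? | Sponsor time limit |
|---|---|---|
| Dosing period, on omeprazole | Not without the code | 24 hours |
| Dosing period, on placebo | Not without the code | None stated |
| Washout, Days 51-64 | Yes, from the calendar | None stated |

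In every row the untimed sponsor route still applies, and so do the 8.5 IRB rules. Neither depends on arm.

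**The case against.** **On the AE table.** The plan does not say that AEs will be pooled; it simply names no treatment column. Onset dates are recorded, so the split can be made after unblinding and nothing is irrecoverably lost. Expected counts are very small. GI symptoms are covered separately by PROMIS forms, and 6.2 lists their exploration on omeprazole versus placebo. Most of this stands, and it is why the point is minor. It does not remove the gap. PROMIS leaves out 5 of the 12 events in 9.4.2 (headache, dizziness, upper respiratory infection, cough, rash). A rule for assigning events to treatment is also better fixed before the code is opened.

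**On 8.6.** A reader might infer that the clause forces staff to break the blind, or that SAEs on placebo go unreported. The documents support neither. Reporting every SAE within 24 hours complies without any code. Washout status is known from the calendar. An unblinding route exists in 9.1.3, although it serves clinical care and is not tied to 8.6. Section 8.6 opens with a general deferral to regulatory and sponsor requirements, which may contain a deadline not visible here. Section 7.1.5 says omeprazole is prescribed for all subjects, and all are due to cross over, so 8.6 may be meant to cover everyone. What stands is narrower: 8.6 does not say so, and its literal trigger cannot be assessed by blinded staff during a dosing period.

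**Conclusion.** Both parts hold on the text. The planned AE summary has no treatment dimension. Followed as written, it mixes omeprazole time (33% to 42% of Days 16-99) with placebo and washout time. The only timed sponsor SAE report rests on a condition that blinded staff cannot check during dosing without the code; on the literal reading, SAEs on placebo or in washout have no stated sponsor time limit.

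Severity is minor. The primary analysis, sample size and power do not change. The 8.6 wording is the weightier part; the missing AE split alone is close to an omitted detail. It would go too far to conclude that the trial cannot describe safety by treatment: the data allow it and only the specification is absent.

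The percentages assume the day numbering in the flow table and full completion of both periods. The range reflects the unresolved end of dosing.

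**What to change.** 1. **Section 8.6.** Replace the omeprazole condition with wording that does not depend on allocation, for example: *any subject who has received study drug (omeprazole or placebo), in any study period including washout*. This fits the AE definition in 8.3 and does not extend 24-hour reporting to pre-dose events.
2. **Section 6.3.3.** Tabulate AEs by treatment at onset (omeprazole, placebo, washout) from the recorded onset date. Use the subjects dosed with each treatment as the treatment denominators, list pre-dose events separately, and report descriptively without tests. Carry the same wording into 5.3 and the synopsis.
3. **End of dosing.** Reconcile 3.1.3, the flow table in 4.1, 4.5 and 7.1.1, then state in 6.3.3 to which period AEs on Days 44-50 and 93-99 belong.

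The cost is a few sentences. The table needs no new data. The one downside is possibly a few more 24-hour SAE reports to the sponsor.

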## 6.4 Sample Size and Power

The primary hypotheses of this study: 1) The use of omeprazole, a proton pump inhibitor medication, in combination with PERT will significantly improve dietary fat absorption compared to placebo in subjects with CF and EPI as indicated by CFA%. Our previous experience in subjects with CF and EPI receiving PERT, CFA% was 81±14% in one study, 83±10% in another, and more recently, 89.5±7.4% in subjects with CF gating mutations and EPI. In comparison, in healthy subjects, CFA% is typically ≥93%. In the study of subjects with gating mutations in which CFA% was assessed before and after 3- months of ivacaftor treatment, there was a significant increase in CFA% of 3.1±3.0% (p<0.01) with ivacaftor treatment in the 15 subjects with EPI and were receiving PERT during the study.

There is limited evidence from randomized placebo-controlled trials that agents such as omeprazole that reduce gastric acidity, when used as adjunctive therapy with PERT are associated with improvement in fat absorption. Heijerman and colleagues, in a randomized controlled trial with a crossover design, found a reduction of 4.8% in fecal fat excretion in 11 subjects receiving 14-days of omeprazole compared to when they received 14-days of placebo (18.1 % vs. 22.9%, respectively). In another study using a similar crossover design, the same authors found a reduction in fecal fat excretion of 8.9%, from 19.6% after 14-day placebo treatment to 10.7% after 14-day omeprazole treatment in 9 subjects on high dose pancreatic enzyme therapy. Proesmans et al, using a randomized crossover design in a study of 15 children with CF and confirmed steatorrhea, found a reduction 7.5 g of fecal fat (from 13.0 to 5.5 g) and an increase in CFA of 7% (from 87 to 94%) after one month of omeprazole use. In other clinical trials of H2 acid blockers as adjunctive therapy to PERT, CFA% improved from 77.1 to 83.6% in a study of 10 children with CF receiving PERT only, compared to PERT plus cimetidine over 14-day periods, and from 74.4% to 87.3% in 10 CF children receiving PERT only and PERT plus famotidine over 6-month periods. In our proposed randomized controlled trial with a crossover design, 22 subjects (11 randomized to 28-day treatment and 11 to placebo at Visit 1, then crossing over to the alternate treatment for 28-days) will have 80% power to detect an increase of 3% with omeprazole treatment compared to no change (0%) when on placebo with a common SD of 5% using a paired t-test with  $\alpha$  =0.05.

We have not based the samples size upon the secondary exploratory hypotheses, however, the effect sizes that can be detected with our sample size of 22 subjects can be estimated. For the MBT method, the sample size is based upon our previous experience in CF with detecting differences in Cmax and AUC for HA and the HA/PA ratio4, and in detecting the percent change in HA absorption (from pharmacokinetic modeling) compared to healthy subjects5. For our proposed study, with the crossover design, 22 subjects (11 in each randomization group) will have 80% power to detect a difference in means of 0.60 (the difference in Cmax (in AUC) HA/PA ratio, with a mean of 1.62 (1.30) for omeprazole treatment, compared to 1.02 (0.70)) for placebo: this is a 37% increase in Cmax and 46% increase in AUC with omeprazole treatment compared to placebo, assuming that the common SD is 0.68 using a paired t-test with  $\alpha$  =0.05. For the CFQ-R domain scores, a sample size of 22 subjects with provide 80% to see an increase of 9 points (i.e. from 80 to 89) with omeprazole treatment compared to placebo with a common SD of 15 points using a paired t-test with  $\alpha$ =0.05. For the SmartPill®, Gelfond has demonstrated significantly lower duodenal pH in subjects with CF compared to healthy controls. The outcome of interest is the time that it takes for the pH to reach 5.5, the minimum level required to dissolve the enteric coating from PERT so that they are effective for nutrient absorption. In a study of 10 subjects with CF compared to 10 healthy controls using the SmartPill® methodology, the time required to reach a pH of 5.5 in CF was 17.7±6.8 compared to  $6.3\pm6.4$  In controls (p=0.004). We expect a subsample of 12 subjects to be 18+ years of age and use the SmartPill® for duodenal pH assessment. A sample of 10 subjects is required for 80% power to see a reduction in time to pH of 5.5 in the GI tract from 17 to 11 minutes

with omeprazole treatment compared to placebo, with a common SD of 7 minutes, using a paired t-test with  $\alpha$ =0.05.

Using this randomized crossover design, a total sample of 22 subjects, 11 in each randomization group will be needed. Therefore, enrolling 24 subjects (12 in each group) will result in 22 subjects completing the study if we experience 10% attrition.

## 6.5 Interim Analysis

No interim analysis is planned.

## 7 STUDY MEDICATION (STUDY DEVICE OR OTHER STUDY INTERVENTION)

## 7.1 Description

Omeprazole is a proton-pump inhibitor that is available both over-the-counter and as a prescription for multiple indications, including treatment in adults of duodenal ulcers, gastric ulcers, and eradication of *Helicobacter pylori* infection, as well as in adults and children for gastroesophageal reflux disease, maintenance of healing of erosive esophagitis, and treatment of hypersecretory conditions. The omeprazole in this study will be overencapsulated so as to be identical to an inert placebo, which will not affect pharmacokinetics or pharmacodynamics.

#### 7.1.1 Packaging

Omeprazole 20mg capsules or an identical placebo will be provided to patients in a medication bottle at Visit 1 and Visit 2. Subjects will be given a 33-day supply for 28 days of use (28 days plus 20% for extra doses). Subjects will return unused capsules to the study team at Visit 2 and Visit 3. All research personnel will be blinded to the randomization throughout the study. In a medical emergency, [name] (or designee) will be unblinded to the participant's study medication at any time, day or night to provide the needed information for clinical care.

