	Visit 2 : Outcomes are measured after the 28 days of treatment or placebo; subjects then cross over to other treatment arm.
	Visit 3 : Outcomes are again measured after another 28 days of treatment or placebo. Once 72-hour stool collection is completed, subjects complete the study and return to normal medication regimen.
Efficacy Evaluations	The efficacy of PPI as adjunct to PERT will be evaluated using the gold standard CFA, as well as the MBT and the SmartPill®.
Pharmacokinetic Evaluations	N/A
Safety Evaluations	Safety will be monitored by adverse events reporting. The frequencies of AEs by type, body system, severity and relationship to study supplement will be summarized. SAEs (if any) will be described in detail.
Statistical And Analytic Plan	Comparison of outcomes by randomization group at each time point: Descriptive statistics for CFA%, duodenal pH and MBT outcomes (mean, standard deviation, median, range, 95% CI) will be calculated and for the total group comparing on and off omeprazole treatment using pair t-tests or Wilcoxon sign rank tests as appropriate. Differences between randomization groups at each time point and differences in the change over time with treatment will be assessed with unpaired t tests or Mann Whitney U rank sum tests as appropriate. For the MBT outcomes, a moment-based pharmacokinetic (PK) analysis will be performed based or non-compartmental methodology using WinNonLin version 9.1 (Pharsight, Cary, NC). Baseline (CO) and maximum (Cmax) plasma concentrations are calculated, and area under the curve from time zero to eight hours (AUC) is calculated using the linear trapezoid method. PK parameters can then be compared for the total group comparing on and off omeprazole using paired t-tests or Wilcoxon sign rank tests as appropriate, and between randomization groups at each time point using an unpaired t-test or Mann Whitney U rank sum test as appropriate. A mixed effects modeling approach will be employed to examine the correlation of subject characteristics (age, BMI, sex, disease status, etc) to CFA%, duodenal pH and to PA and HA exposure metrics derived from the non-compartmental analysis to assess change over time in MBT response to PERT administration in subjects with CP. Metrics to be tested will be CFA%, PA and HA Cmax, AUC, HA/PA Cmax and AUC ratio and the %HA

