## 3.1.2 Study Treatment Phase (start of the study intervention)

There will be a 14-day period prior to the start of the study intervention during which time all subjects will maintain a standard diet/PERT dose. Subjects who were taking PPIs or H2 medication at the time of the screening/consent visit, will discontinue these medications for the duration of the study. This 14-day period prior to the start of the intervention will also serve as a washout period from these medications for these subjects. After this 14-day period, treatment with omeprazole or placebo will commence. After completing 28 days of treatment with omeprazole or placebo, subjects will have a second study visit, during which the first set of assessments will be completed. All study visits will occur at outpatient research offices of the Center for Human Phenomic Science (CHPS) at The Children's Hospital of Philadelphia (CHOP), a pediatric health care center. Eligible subjects will be enrolled into the study and come to CHOP for the study visits. Refer to Table 1 for list of assessments and the study timeline for the pace of recruitment.

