## 3.1.3 Second Treatment Phase

After completing the second study visit, there will be a 14-day washout period during which subjects will discontinue their study medication but continue their standard diet/PERT use. Subjects will then cross over to the other treatment arm and undergo an additional 28 days of treatment with omeprazole or placebo. At the end of this treatment period, they will have a third study visit that will include the outcome measure assessments.

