#### 3.3 Study Duration, Enrollment and Number of Sites

## 3.3.1 Duration of Study Participation

The study duration per subject will be up to 100 days, with one day for screening and consent, up to 48 days each for Phases 1 and 2 for the washout and treatment periods, as well as the assessment visits, totaling approximately 100 days. No follow-up is required upon completion of the study procedures.

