## 4 STUDY PROCEDURES

## 4.1 Consent Visit (Visit 1)

- Review of health history including prior and concomitant medications
- Review demographics
- Informed Consent
- Review of diet pattern
- Subjects asked to maintain a moderate to high fat diet throughout the study
- Subjects asked to maintain their clinically established PERT dose throughout the study
- Subjects asked to wean PPI or H2-receptor antagonist medication, if taking
- Simple anthropometrics
- Stool collection if needed
- Sexual maturity self-assessment (age <18y, n=12)

- GI symptom questionnaire
- Urine pregnancy test (female subjects)
- Distribute arm 1 study medication

Protocol	Day 1	Da	ys 2-15			Day	/s 16-43					
Visit 1: Consent and Randomization	- Clarify diet & PERT - Questionnaires - Elastase (if needed)			l-day washout p RA medication, i Istain on standar h fat diet onfirm standardi	f applicable rd moderate	to	- Randomized treatment to either omeprazole (PPI) or placebo for 28 days					
	Day 44	Day 45		Day 46	Day 47	Day	48	Day 49	Day 50	Days 51-		
Visit 2: After 28-day treatment with PPI or placebo	- Fast from 8pm - No dairy - Remain on standard PERT	- MBT - 7am-4p - Serum la - Anthros  If ≥18 yea - SmartPil - Fast fror 12am	bs a rs: ll	- Resume moderate- high fat diet If ≥18 years: - SmartPill at 8am - 6hr fast	- Diet record (day 1)	- Die reco (day - 72 Stoo (day	ord v 2) -hr ol	- Diet record (day 3) - 72-hr Stool (day 2)	-72-hr Stool (day 3)	- 14-day washout period from treatment placebo		

	Days 65-92	2 – Randomized	crossover treatn	nent (PPI to p	lacebo, or pla	acebo to PPI)	for 28 days	
	Day 93	Day 94	Day 95	Day 96	Day 97	Day 98	Day 99	Day 100
Visit 3:  After 28-day crossover treatment with placebo or PPI	- Fast from 8pm - No dairy - Remain on standard PEM	-MBT - 7am-4pm -Serum labs - Anthros  If ≥18 years: - SmartPill - Fast from 12am	- Resume moderate- high fat diet If ≥18 years: - SmartPill at 8am - 6hr fast	- Diet record (day 1)	-Diet record (day 2) - 72-hr Stool (day 1)	-Diet record (day 3) - 72-hr Stool (day 2)	-72-hr Stool (day 3)	- Return to usual care and medication regimen - Return to usual diet

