## 4.2 Study Treatment Phase

After the screening and consent visit, subjects will have two visits in this study. Visit 2 will be after 28 days of either omeprazole or placebo. After a 14-day washout period from study intervention of either treatment or placebo, subjects will cross over to the opposite treatment and receive the alternate therapy for 28 days. Visit 3 will take place at the completion of this 28-day period of either treatment or placebo. Assessments at both Visit 2 and 3 are identical.

#### 4.2.1 Visit 2

Visit 2 takes place over seven total days, detailed below:

#### Day 1

- Regular lunch/dinner except for no intake of dairy products
- No alcohol intake
- Normal daily activity
- Fast overnight starting at 8pm

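### Study drug is scheduled for 28 days and supplied for 33, but dosing through the primary stool collection takes 35, so CFA may not be measured on treatment

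*Combined protocol and SAP*

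**What the plan says.** The protocol describes the length of dosing in two ways.

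**Dosing for 28 days, with assessments afterwards.** The flow table in Section 4.1 lists, for Days 16–43, "Randomized treatment to either omeprazole (PPI) or placebo for 28 days", and gives Days 65–92 to the crossover treatment. Section 3.1.2 says "After completing 28 days of treatment with omeprazole or placebo, subjects will have a second study visit". Section 4.2 says "Visit 3 will take place at the completion of this 28-day period of either treatment or placebo". Section 3.3.1 allows "up to 48 days each for Phases 1 and 2 for the washout and treatment periods, as well as the assessment visits", which lists treatment and assessment separately. Section 7.1.1 sets the supply: "Subjects will be given a 33-day supply for 28 days of use (28 days plus 20% for extra doses"). Section 7.1.3 sets the dose at 20 mg daily, which is one capsule.

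**Dosing until the collections are finished.** Section 3.1.3 says that, once the second visit is complete, "there will be a 14-day washout period during which subjects will discontinue their study medication". Section 4.2.1 defines that visit as seven days, and the flow table starts the washout on Day 51. Section 4.5 ends omeprazole when every Visit 3 collection is done. The synopsis, under Visit 3, says "Once 72-hour stool collection is completed, subjects complete the study and return to normal medication regimen".

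The day-by-day lists in Sections 4.2.1 and 4.2.2 cover diet, fasting, food records, stool and the event diary. They never tell subjects to take study drug on Days 44–50 or 93–99.

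On returns, Section 7.1.1 says "Subjects will return unused capsules to the study team at Visit 2 and Visit 3", and Section 7.1.4 agrees. Section 7.1.5 puts the return of leftover drug at study completion.

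**The concern.** Section 5.2.1 defines the primary comparison as CFA on PPI plus PERT against CFA on placebo plus PERT. That comparison needs subjects to be taking the assigned capsule while the recorded meals are eaten and the stool is collected. The written schedule and the bottle size do not secure this, and no instruction fills the gap.

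If some subjects stop at 28 days and others continue, the omeprazole CFA values mix measurements made on drug with measurements made after it was stopped. The analyst could not separate them, because the protocol does not ask for the date of the last capsule.

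There is also a practical hazard. The arm 2 bottle is handed out on the Visit 2 clinic day (Day 45), before the first-period stool collection. It holds the opposite treatment in identical capsules under identical labelling (Sections 7.1.2 and 9.1.2). A subject who runs out on Day 48 has that bottle at home, and nothing explicitly says to leave it closed until Day 65.

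**Working it through.** **Inputs**
- One capsule daily (Section 7.1.3); 33 capsules per period (Section 7.1.1).
- First dose on Day 16 in period 1 and Day 65 in period 2; scheduled last dose on Day 43 and Day 92 (flow table, Section 4.1).
- MBT on Day 45/94; SmartPill on Day 46/95; food records on Days 47–49/96–98; stool on Days 48–50/97–99 (flow table; Sections 4.2.1 and 4.2.2).
- Washout starts on Day 51 (flow table).

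**The plan's own figure.** 28 × 1.20 = 33.6, stated as 33. The figure reproduces, rounded down. The actual overage is 5/28 = 17.9%.

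**Doses needed** = last day − first day + 1. **Day of the last capsule** = first day + 32.

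| | Period 1 | Period 2 |
|---|---|---|
| Scheduled doses | 43 − 16 + 1 = 28 | 92 − 65 + 1 = 28 |
| Through last recorded meal day | 49 − 16 + 1 = 34 | 98 − 65 + 1 = 34 |
| Through last stool day | 50 − 16 + 1 = 35 | 99 − 65 + 1 = 35 |
| Day of 33rd capsule | 16 + 32 = 48 (stool day 1) | 65 + 32 = 97 (stool day 1) |
| Shortfall, meals / stool | 34 − 33 = 1 / 35 − 33 = 2 | 1 / 2 |

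**Reading A: stop after 28 days.** Time from the last capsule to each measurement in period 1 (period 2 is the same):
- MBT: 45 − 43 = 2 days
- SmartPill: 46 − 43 = 3 days
- Recorded meals: 47 − 43 to 49 − 43 = 4 to 6 days
- Stool: 48 − 43 to 50 − 43 = 5 to 7 days

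**Reading B: dose to the stated stopping points.** A subject who misses nothing takes the last capsule on stool day 1. Stool days 2 and 3 and the last recorded meal day are uncovered. If unused capsules are handed back on the only clinic day common to all subjects (Day 45/94), and that day's dose is the last, the gap to the stool days is 48 − 45 to 50 − 45 = 3 to 5 days.

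**Which reading fits the washout.** Days 51–64 are 64 − 51 + 1 = 14 drug-free days, which matches the stated washout. Stopping on Day 43 would give 64 − 44 + 1 = 21. The 14-day figure therefore fits only Reading B.

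**What the capsule count can show.** Five capsules returned means 33 − 5 = 28 taken. That fits full adherence with a stop on Day 43. It also fits dosing over Days 16–48 (33 days) with five doses missed. The same 28 doses are 28/28 = 100% of one denominator and 28/35 = 80% of the other.

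**The case against.** The two readings exclude each other, so no subject suffers both defects. If the stopping points govern, the protocol does say when to stop, and only a shortfall of two capsules remains. That shortfall needs perfect adherence: a subject who misses two of 35 doses (33/35 = 94%) has enough to reach Day 50. Section 7.1.4 also provides for phone or text contact to check supply, and for calendars. Adherence is asked about at Visits 2 and 3 and by phone (Section 5.1.3, Table 1), so the count does not stand alone. The protocol sets no adherence threshold that the 100% versus 80% contrast would affect. Finally, the documents say nothing about how long omeprazole acts after the last dose, so no bias in CFA has been demonstrated.

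Much of this is fair. The shortfall is conditional, the size of any lost effect is unknown, and the requirement for 35 doses is inferred from the stopping points and not stated in any one sentence. The inference from Section 3.3.1 is also weak: 48 − 14 − 28 leaves 6 days, yet the visit lasts seven and each calendar phase (Days 2–50 and 51–99) runs 49 days.

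The conflict remains, because each reading fails by itself. The 28-day schedule measures the omeprazole CFA days after the last capsule. The later stopping point leaves the fully adherent subject without enough drug. Phone calls and calendars add no capsules, and none of the listed adherence checks specifies a last-dose date. The 20% overage is described as extra doses, and even if it was meant for the assessment week, five spare capsules do not cover seven days.

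**Conclusion.** The concern holds and should be fixed. The schedule (28 doses) and the supply (33) conflict with the protocol's own stopping points (35) over exposure during the primary measurement. Followed literally, the 28-day schedule puts the stool collection 5–7 days after the last capsule and the recorded meals 4–6 days after it. Under the later stopping point, a fully adherent subject is one capsule short for the meals and two short for the stool.

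The day counts rest on one capsule daily starting on Day 16 and Day 65; the running-out date also assumes none missed or lost. Whether and how far this dilutes the CFA difference depends on the duration of effect after the last dose, which the documents do not give. No loss of power is claimed.

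**What to change.** - State in the flow table and in Sections 3.1.2, 3.1.3, 4.2, 5.2.1 and 7.1 that study drug is taken daily for 28 days before the assessments and continues through the last stool day (Day 50 and Day 99), 35 doses per period.
- Dispense at least 35 capsules per period, or 35 × 1.2 = 42 with the protocol's own overage.
- Have unused capsules returned with or after the stool collection, and align Sections 7.1.1, 7.1.4 and 7.1.5 on that.
- Tell subjects not to open the arm 2 bottle before Day 65.
- Record the date of the last capsule in each period on the case report form, and calculate adherence against 35 doses.

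The cost is 35 − 33 = 2 more capsules per period (42 − 33 = 9 with the overage), one case report form field, and protocol and consent wording that gives 35 days of dosing. The 14-day washout on Days 51–64 and the visit calendar stay as they are, and no visit is added.
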